**3. STUDY DESIGN AND RATIONALE****3.1. Overview of Study Design**

This is a randomized, open-label, active-controlled, multicenter study designed to assess the efficacy and safety of trabectedin+DOXIL as a third-line chemotherapy in subjects with platinum-sensitive advanced-relapsed epithelial ovarian, primary peritoneal, or fallopian tube cancer who received 2 previous lines of platinum-based chemotherapy. Approximately 670 adult subjects will be enrolled in this study, with 335 subjects per planned treatment group. At randomization, subjects will be stratified by 4 criteria: 1) the time from the last dose of first-line platinum therapy to disease progression (6 months to 12 months vs >12 months to 24 months vs >24 months), 2) Eastern Cooperative Oncology Group (ECOG) performance status grade (0 vs 1), 3) BRCA 1/2 status (mutation vs no mutation), and 4) prior DOXIL therapy (no vs yes). Subjects will then be randomly assigned in a 1:1 ratio to the trabectedin+DOXIL combination therapy group (Arm A) or to the DOXIL monotherapy group (Arm B).

During the treatment phase, subjects will receive study drug by IV infusion on Day 1 of a 21-day cycle in Arm A and on Day 1 of a 28-day cycle in Arm B. Treatment will continue until the occurrence of disease progression or unacceptable treatment toxicity, or until 2 cycles after assessment of a complete response (CR). Subjects assigned to the trabectedin+DOXIL group (Arm A) will be pretreated with 20 mg of dexamethasone IV, or an equivalent IV corticosteroid, approximately 30 minutes prior to initiation of infusion of DOXIL on Day 1 of each treatment cycle.

Subjects will be followed for survival at least every 8 weeks for the first 2 years after the treatment termination visit and approximately every 12 weeks thereafter. This study will end 2 months after the last subject has received the last dose of study drug, when 514 deaths have been observed, or until the clinical cutoff date.

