### **9.1.3.4. Tumor Assessment**

Measurable disease and the response criteria used in this protocol are defined in the RECIST guidelines (Version 1.1) ([Attachment 2](#)) and will be based on radiologic assessment only.

Every effort should be made to ensure that the same radiographic method of disease assessment (computed tomography [CT] scans or magnetic resonance imaging [MRI]) be used throughout the study. Disease assessment procedures to evaluate objective response must be consistent with RECIST (Version 1.1) guidelines for radiologic assessment, as presented in [Attachment 2](#), RECIST Guidelines. The disease assessments should include, at a minimum, imaging of the chest (with lung views) abdomen, and pelvis. All disease assessments, including CA-125 measurements, will be performed within 30 days before randomization, every 8 weeks ( $\pm 5$  days) from the date of randomization for the first 4 assessments, and then every 12 weeks ( $\pm 5$  days) until disease progression is radiographically confirmed, the start of subsequent anticancer therapy, withdrawal of subject consent, or the clinical cutoff date. Disease assessments should be performed at the treatment termination visit and according to schedule thereafter if disease progression or follow-up therapy has not been documented. Every effort should be made to ensure that these assessments are done on the required date, although a window of  $\pm 5$  days will be accommodated.

In case of clinical progression, radiologic assessments should proceed according to the original Time and Events Schedule or as clinically indicated. The date of progression will be defined as the date of the first imaging study that documents progression.

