## Follow-up Data Collection after Treatment Termination

As of Amendment 6, follow-up data will no longer be collected.

Follow-up assessments for survival status should occur at least every 8 weeks for the first 2 years after the treatment termination visit and then approximately every 12 weeks thereafter, until death or the clinical data cutoff date. Any clinically significant abnormalities persisting at 30 days after the last dose of study drug will be followed by the investigator until resolution or until a clinically stable endpoint is reached. Drug-related Grade 3 or Grade 4 toxicities will be monitored until Grade 2 or less, or for a maximum of 6 months after the last dose of study drug, whichever occurs first. Grade 2 to 4 liver or cardiac toxicities will be monitored until Grade 1 or less, or for a maximum of 6 months after the last dose of study drug, whichever occurs first.

Disease assessments (including CA-125) will be performed using the same radiographic technique (CT scans or MRI) approximately every 8 weeks after randomization for the first 4 assessments and then approximately every 12 weeks until disease progression is radiographically confirmed, the start of subsequent anticancer therapy, withdrawal of subject consent, or the clinical cutoff date. Subjects who have disease progression at treatment termination should continue to be followed for survival and the start of subsequent anticancer therapy. Every effort should be made to record all subsequent anticancer therapies, along with their dates of administration.

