#### **Adverse Events**

The verbatim terms used in the CRF by investigators to identify adverse events will be coded using the Medical Dictionary for Regulatory Activities (MedDRA) and will be graded according to the NCI-CTCAE, Version 4.0. All reported adverse events with onset during the treatment phase (ie, those events that occur or worsen on or after the first dose of study drug up through 30 days after the last dose of study drug) will be included in the analysis. Adverse events will be summarized by MedDRA system organ class and preferred term. For each adverse event, the percentage of subjects who experience at least 1 occurrence of the given event will be summarized overall and by treatment group. Serious adverse events and deaths will be listed. All adverse events resulting in discontinuation of study treatment, dose modification, the interruption of dosing, or a delay in treatment with the study drug will be listed and summarized by preferred term.

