**12.3. Procedures****12.3.1. All Adverse Events**

All adverse events and special reporting situations, whether serious or non-serious, will be reported from the time a signed and dated ICF is obtained until 30 days after the administration of the last dose of study drug or until the scheduled treatment termination visit on or prior to 18 January 2018. Any drug-related Grade 3 or 4 toxicities will be followed by the investigator until Grade 2 or less, for a maximum of 6 months after the last dose of study drug, or until the scheduled treatment termination visit on or prior to 18 January 2018, whichever occurs first. Grade 2 to 4 liver or cardiac toxicities will be monitored until Grade 1 or less, for a maximum of 6 months after the last dose of study drug, or until the scheduled treatment termination visit on or prior to 18 January 2018, whichever occurs first.

Serious adverse events, including those spontaneously reported to the investigator within 30 days after the last dose of study drug, must be reported using the Serious Adverse Event Form. The sponsor will evaluate any safety information that is spontaneously reported by an investigator beyond the time frame specified in the protocol. All events that meet the definition of a serious adverse event will be reported as serious adverse events, regardless of whether they are protocol-specific assessments.

All adverse events, regardless of seriousness, severity, or presumed relationship to study drug, must be recorded using medical terminology in the source document and the CRF. Whenever possible, diagnoses should be given when signs and symptoms are due to a common etiology (eg, cough, runny nose, sneezing, sore throat, and head congestion should be reported as "upper respiratory infection"). Investigators must record in the CRF their opinion concerning the

relationship of the adverse event to study therapy. All measures required for adverse event management must be recorded in the source document and reported according to sponsor instructions.

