## 2. ANALYSES PLANNED

### 2.1. General Analysis Definitions

#### 2.1.1. Definition of Cycle, Treatment Phase, Baseline

**Cycle:** The duration of cycles may not consistently be as the planned 21 days in the trabectedin + DOXIL Arm or 28 days in the DOXIL Arm, it will depend on the earliest date of the DOXIL/trabectedin doses given in the next cycle. If a subject experiences toxicity at the planned start of a cycle that leads to a delay in DOXIL/trabectedin administration, this new cycle will be delayed, and the previous cycle will be prolonged (without additional DOXIL or trabectedin treatment).

The start of the cycle is the date of the first administration of DOXIL or trabectedin in a cycle. The end of a cycle is the day before the first infusion of the immediate subsequent cycle recorded on the case report form (CRF).

The last cycle ends 3 weeks after the start of this cycle for the trabectedin + DOXIL Arm, and 4 weeks for the DOXIL Arm.

The assessments performed during the 'End-of-treatment visit' will be included in the last treated cycle for analysis.

All lab samples taken after the last treatment and up to 30 days after the last DOXIL/trabectedin infusion will be captured in the last cycle.

**End-of-treatment phase:** The end of the treatment phase is the date the last cycle ends, i.e., 3 weeks after the first trabectedin or DOXIL dosing in the last cycle for Arm A, or 4 weeks after the dose of DOXIL in the last cycle for Arm B.

YONDELIS®: Statistical Analysis Plan Study ET743-OVC-3006

**Follow-up phase:** Following termination of DOXIL/trabectedin treatment, subjects are followed every 8 weeks for survival for the first 2 years after randomization and every 3 months thereafter until death or the clinical cut-off date defined at the time when 514 deaths are observed, whichever is sooner. If disease progression has not occurred at treatment termination, then disease assessment should continue every 8 weeks until there is evidence of disease progression or death, or until the clinical data cut-off date, or until the start of first subsequent therapy for ovarian cancer, whichever is earlier. Disease assessment will also be done if necessary to confirm response or document disease progression.

**Relative day:** Assessments will be presented chronologically by cycle day or study day, which are defined in the following:

Cycle day = assessment date - date of first DOXIL or trabectedin infusion for the cycle + 1

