#### **2.2.9. Safety**

##### **2.2.9.1. Adverse Events**

Treatment emergent adverse events will be summarized by disease group and overall. A treatment-emergent adverse event is defined as any AE occurring or worsening on or after the first treatment of DOXIL/Trabectedin, and within 30 days after the last dose. For imputation rules for incomplete dates, see Attachment 4.1.

Adverse events are documented on the CRF together with their severity, according to the NCI CTC version 4.0, also referred to as NCI toxicity grading. For the categorization of the adverse events, the MedDRA dictionary will be used. Adverse events are considered drug related when the relation to trial medication is considered to be possible, probable, or very likely, according to the investigator's opinion.

Summary of overall adverse events will be done by body system and preferred term, by severity (worst toxicity grade), by relationship to the study drugs (trabectedin or DOXIL), and by AE outcome. Tables will be sorted by body system/preferred term and by the highest incidence. In the AE database, "neoplasm malignant aggravated", and "condition aggravated" are created terms to match the Global Medical Safety (GMS) death reporting database (in case of death due to disease progression). These will not be included in the AE summaries.

A listing will be prepared on all adverse events. If data is available, a listing for delayed adverse events (defined as new onset of AE occurring 30 days after last dose as judged by investigator to be related to trial medication) will be presented.

YONDELIS®: Statistical Analysis Plan Study ET743-OVC-3006

First occurrence of grade 3 and 4 adverse events will be reported by cycle. The drug related grade 3 and 4 adverse events would be summarized.

A frequency table will be made for the AEs leading to cycle delay, dose reduction, skipped dose, or withdrawal of study medication. Adverse events leading to permanent stop and AE with outcome death will also be presented by drug relatedness.

For all serious adverse events (SAEs), the investigator has to send an SAE form to the Janssen R&D GMS. The AEs that are indicated on the CRF as serious are used for the summary tables. A summary table by any grade SAEs will be presented. A similar table will be presented for the drug-related SAEs.

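### The 30-day adverse event window does not stop at the next anticancer therapy, so next-line toxicity can enter the by-arm safety tables

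*SAP*

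**What the plan says.** SAP 2.2.9.1 counts as treatment-emergent "any AE occurring or worsening on or after the first treatment of DOXIL/Trabectedin, and within 30 days after the last dose". Protocol 11.7 (Adverse Events) analyses events that "occur or worsen on or after the first dose of study drug up through 30 days after the last dose of study drug". Collection under Protocol 12.3.1 covers the same period, "until 30 days after the administration of the last dose of study drug", subject to the January 2018 cutoff. None of the three mentions subsequent anticancer therapy.

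The efficacy rules do. In SAP 2.2.8.4, progression or death after the start of subsequent ovarian cancer therapy is not a PFS event, and the subject is censored at the last earlier scan. In SAP 2.2.8.3.2, best overall response is closed at progression or at the start of subsequent therapy.

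Dosing is "on Day 1 of a 21-day cycle in Arm A and on Day 1 of a 28-day cycle in Arm B". For the final cycle, SAP 2.1.1 states: "The last cycle ends 3 weeks after the start of this cycle for the trabectedin + DOXIL Arm". It allows 4 weeks for the DOXIL arm.

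Start dates of next therapy are available. Protocol 9.1.4 asks that "Every effort should be made to record all subsequent anticancer therapies, along with their dates of administration", and SAP 2.2.8.9 lists the start date.

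**The concern.** A switch before day 30 is possible under these documents. No section sets a minimum gap between the last study dose and the next regimen. Protocol 10.2 lists starting another anticancer therapy as a reason to stop study treatment. Protocol 9.1.3.4 conditions scans around and after the termination visit, which falls 30 to 33 days after the last dose, on the case "if disease progression or follow-up therapy has not been documented". The date rule in SAP 4.1 can place an incomplete next-therapy start one day after a study dose. The trial's own entry washout from prior chemotherapy is 3 weeks (exclusion criterion 7.1), which is shorter than 30 days.

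For such a subject, the remaining days of the window hold the toxicity of another regimen, and the all-cause tables attribute it to the randomised arm. At stake is how the final comparative safety record is read. Because the two arms have different cycle lengths and share one scan calendar, the overlap need not be equal between them.

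**Working it through.** The plan states no figure on this point, so there is nothing to reproduce. The check is window arithmetic.

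**Formula.** Let x be the days from last dose to the start of next therapy. The overlap is max(0, 30 − x). Counting both the start day and day 30 would add one day to each non-zero result.

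**1. Against the planned end of the last cycle.** The window extends 30 − 21 = 9 days past it in Arm A and 30 − 28 = 2 days in Arm B. If next therapy starts d days after that point, the overlap is max(0, 9 − d) against max(0, 2 − d): 9 vs 2 at d = 0, 7 vs 0 at d = 2, 2 vs 0 at d = 7, and 0 vs 0 from d = 9.

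**2. Against the scan calendar, everything on schedule.** Scans fall at weeks 8, 16, 24, 32, 44 and 56 (days 56, 112, 168, 224, 308, 392). Assume that the first dose is on the day of randomisation and that each scan is read before any dose due that day. The days k from last dose to scan are the remainder of the scan day divided by the cycle length, or a full cycle if the remainder is 0.

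- Arm A: k = 14, 7, 21, 14, 14, 14, leaving 16, 23, 9, 16, 16, 16 open days.
- Arm B: k = 28 each time, leaving 2 open days.

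With a lag of L days from scan to next therapy, the overlap is max(0, 30 − k − L). L is an assumption. L = 7 gives 9, 16, 2, 9, 9, 9 against 0. L = 14 gives 2, 9, 0, 2, 2, 2 against 0.

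**3. With permitted variation.** Arm B's zero arises because every scan week is a multiple of 4, so each scan lands on an Arm B dosing day. The protocol allows scans ±5 days and a first dose up to 7 days after randomisation. Mean overlap in days, A vs B, averaged over whole-day shifts and the six scans:

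| Timing | L = 7 | L = 14 |
|---|---|---|
| On schedule | 9.0 vs 0 | 2.8 vs 0 |
| First dose 0-7 days after randomisation | 12.1 vs 0.4 | 5.5 vs 0 |
| Scan ±5 days only | 10.6 vs 9.1 | 4.2 vs 5.9 |
| Both | 12.3 vs 4.5 | 5.7 vs 2.3 |
| Scan uniform within the cycle | 12.50 vs 9.45 | 6.10 vs 4.57 |

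The third row shows why the direction is fragile. An Arm B scan 1 to 5 days late falls after the next dose, so k is 1 to 5 and 29 to 25 days remain open. At L = 14 these five shifts give 15 + 14 + 13 + 12 + 11 = 65 days and the other six give 0, so the mean is 65/11 = 5.9, above Arm A's 4.2. At L = 7 the sum is 100, and 100/11 = 9.1.

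**4. Scan uniform in the cycle, switch uniform 7 to 21 days later.** The share switching within 30 days is 1 − 72/294 = 75.5% in Arm A and 1 − 168/392 = 57.1% in Arm B. Mean overlap is 6.5 vs 4.9 days.

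**5. Same interval after the last dose in both arms.** There is no difference: 9 vs 9 at day 21, 2 vs 2 at day 28, and 0 vs 0 after day 30.

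Dosing delays of up to 3 weeks (Protocol 6.1) and the +2-day dosing window are not modelled separately. They would move results toward the uniform row.

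**The case against.** The fixed window has real merits. It gives both arms the same follow-up after the last dose, and it matches the collection period (Protocol 12.3.1), the 30-day rule for deaths as serious events (Protocol 12.3.2) and the death tables (SAP 2.2.9.4). SAP 2.2.9.1 also summarises events by relationship to study drug, including drug-related grade 3-4 and serious events, which screens out part of the problem. Truncating the main table would shorten observation, possibly more in Arm A. Keeping post-switch events only when judged related would rest on investigator attribution in an open-label trial. These arguments stand against replacing the main definition. They do not cover the all-cause tables, which have no screen, and the existing relatedness tables depend on the same open-label attribution.

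A reader might go further and infer that the leak is built into the design against Arm A, from 9 to 23 open days against 2. The documents do not support that. The contrast needs exact scheduling and a scan read before dosing. It narrows or reverses within the permitted windows, and it vanishes if both arms switch at the same interval after the last dose.

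A reader might also infer that the window tainted the stopping decision, since higher Arm A toxicity was one of the two stated grounds. The IDMC cited toxicity that was expected as well as observed. The prior trial in Protocol 1.2.2 showed grade 3-4 neutropenia of 63% vs 23% and ALT elevation of 32% vs 1%. Nothing indicates that a few days of overlap influenced the recommendation.

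**Conclusion.** The point holds as a gap in the safety definition. All-cause adverse event, grade 3-4 and serious event tables can include next-line toxicity for anyone who switches within 30 days of the last dose, while PFS and best overall response are protected from it.

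The only imbalance that follows from the plan itself is 9 vs 2 days past the planned end of the last cycle. In the scan-based scenarios above with a 7- or 14-day lag, mean overlap per switcher ranges from about 3 to 12.5 days in Arm A and from 0 to about 9.5 days in Arm B. Arm A is usually the larger, but not always. These are days at risk among assumed early switchers, not events. The number of misattributed events cannot be computed, because the documents give neither the time to next therapy by arm nor event rates on it. A larger effect in Arm A is therefore possible but not shown.

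**What to change.** Keep the 30-day tables as they are. Add to SAP 2.2.9.1 a second set of by-arm tables (treatment-emergent, grade 3-4 and serious events) whose window ends at the earlier of 30 days after the last dose and the day before the first subsequent anticancer therapy. Retain in them any later event within 30 days that the investigator judges related to study drug. Flag the remaining post-switch events in a listing. Cross-refer from the text to the 30-day window in Protocol 11.7, so that it is clear which set is the main one.

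The cost is one derived flag and a few extra tables from start dates already collected. Some late study-drug reactions judged unrelated would drop out, but only from the truncated version. Incomplete start dates imputed under SAP 4.1 can fall as early as the day after a dose and would then cut the window short. Imputed dates should therefore be marked in the listing.

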### **2.2.9.2. Clinical Laboratory Tests**

#### **2.2.9.2.1 Hematology**

Laboratory results will be classified according to the NCI CTC version 4.0 as described in the attachment of the protocol. For absolute neutrophil count (ANC), platelet count and hemoglobin, the worst grade per subject will be tabulated overall during treatment and per cycle.

Cross tabulation will be presented for the worst grade during treatment versus the baseline toxicity grading.

All data will be listed. In addition, a listing will present subjects' data by cycle and laboratory test for those whose laboratory values reach grade 4 anytime during the trial.

#### **2.2.9.2.2 Serum chemistry**

Similar to hematology analysis, the worst grade during treatment will be cross tabulated to the baseline grade for sodium, alanine aminotransferase [ALT], potassium, total bilirubin, direct bilirubin, blood urea nitrogen [BUN], alkaline phosphatase [ALP], creatinine, creatine phosphokinase [CPK], glucose, albumin, aspartate aminotransferase [AST], and total protein).

Cross tabulation will be presented for the worst grade during treatment versus the baseline toxicity grading.

All data will be listed. In addition, a listing will present subjects' data by cycle and laboratory test for those whose laboratory values reach grade 4 anytime during the trial.

YONDELIS®: Statistical Analysis Plan Study ET743-OVC-3006

#### **2.2.9.2.3 Hy's Law Cases Analysis**

For subjects with any elevated AT (AST or ALT) of >3xULN, ALP <2xULN, and associated with an increase in bilirubin  $\geq 2$ xULN, a listing for all subjects with all such records will be produced and a summary table of number of such subjects by treatment arm will also be generated.

#### **2.2.9.3. Vital Signs and Physical Examination Findings**

Vital signs (pulse and blood pressure, as well as temperature) and body weight will be measured during the screening phase (within 14 days of randomization). Tabulation will be made summarizing the vital signs and the body weight.

A physical examination will be done during the screening phase (within 14 days of randomization).

